Patients will be monitored for safety throughout the duration of the study. Safety assessments will include vital signs, clinical laboratory assessments (serum chemistry, hematology, coagulation, and urinalysis), physical examinations, neurological assessments (twice weekly on study treatment), prior and concomitant medication reporting, and adverse event reporting. A 12-lead electrocardiogram (ECG) will be performed at Baseline (pre-dose), EOST, and 4 weeks after EOST, or Early Termination. A dilated fundoscopic examination will be performed at least once during the baseline period, which exclusively for this assessment may be up to Day 3 of the study. Follow-up fundoscopic examinations are required at EOST, and 4 weeks after EOST, or Early Termination for those patients who had positive findings up to Day 3 (or more if clinically indicated). A urine pregnancy test (for females of childbearing potential only) will be performed at Screening and Baseline (pre-dose), every 30 days during treatment if required by local regulations, at EOST, and 2 and 4 weeks after EOST, or Early Termination.

In the event of an inadequate response/failure on APX001 study treatment, the study drug may be discontinued and alternative antifungal treatment instituted.

Plasma samples for PK (APX001 [prodrug] and APX001A [active moiety]) will be collected at Baseline (pre-dose), twice weekly during Study Drug Treatment, and at EOST, 2 weeks after EOST, or Early Termination. Plasma samples for PK will be collected at the same time as samples are collected for the study's clinical laboratory assessments. Serum samples for (1,3)- β -D-glucan levels will be collected at Baseline (pre-dose) and EOST, or Early Termination (if applicable).

[figure not shown]
Optionally, if body fluids are sampled as part of routine patient management (e.g. bronchoalveolar lavage, lumbar puncture, paracentesis, vitreous fluid collection, abscess drainage) within approximately 2 hours of blood sampling for PK, these samples may be stored for future analysis of APX001 and APX001A levels.

The evaluation of treatment outcome will be assessed at EOST, and 2 and 4 weeks after EOST, or Early Termination.

The end of study will occur after the last visit of the last patient on the study.

A schematic representing the study's design [follows](#).

Figure 1. APX001-203 Study Schematic

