6.5.3 Early Termination Visit and Withdrawal Procedures

For patients who are withdrawn from the study prior to completion, all EOST procedures will be performed at an Early Termination visit. These procedures include the following:

- Collect blood culture for *Candida* spp.
- Collect other cultures and histopathology from other sites, as clinically indicated
- Perform imaging tests as clinically indicated to monitor the site(s) and extent of invasive candidiasis infection
- Perform dilated fundoscopic examination (only required in those patients who had baseline positive fundoscopic findings [up to Day 3], or as clinically indicated)
- Intravascular catheter management log, as clinically indicated
- Record vital signs, including temperature, blood pressure, heart rate, respiratory rate, oxygen saturation, and weight

- Perform clinical laboratory assessments (serum chemistry, hematology, coagulation and urinalysis)
- Perform 12-lead ECG
- Perform urine pregnancy test (for females of childbearing potential only)
- Perform neurological examination
- Perform focused, symptom-based physical examination, as clinically indicated
- Collect plasma sample for PK (APX001 [prodrug] and APX001A [active moiety])
- Collect serum sample for analysis of(1,3)- β -D-glucan
- Evaluate treatment outcome
- Record concomitant medications
- Assess adverse events

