### 6.4 Definitions for Efficacy Assessments

#### 6.4.1 At EOST

Treatment Success is defined as meeting all of the following criteria:

- Two consecutive blood cultures negative for *Candida* spp., and/or for patients with a deep-seated site of infection, at least one negative tissue culture or aspirate/fluid culture;
  - For patients with a deep-seated site of infection involving visceral organs from which a tissue culture is not obtainable, resolution of the attributable clinical signs of infection recorded at Baseline, and, as applicable, radiological improvement associated with the site of infection is required
- Alive at EOST;
- No concomitant use of any other systemic antifungal therapies through EOST.

Note: administration of another systemic antifungal immediately following EOST for suspected or documented *Candida* infection at any site does not constitute a treatment success at EOST.

Treatment Failure is defined as any case that does not meet the criteria for Treatment Success.

Successful Mycological Outcomes:

- Eradication is defined as a negative blood (and/or other infection site) culture(s) for *Candida* spp. in the absence of concomitant antifungal therapy through EOST;
- Presumed Eradication (applicable to invasive candidiasis) is defined as clinical resolution of invasive *Candida* spp. infection where tissue samples are unavailable (supported by evidence of resolution/improvement in the diagnostic parameters used at Baseline).

Both of the above definitions are in the absence of concomitant or additional systemic antifungal therapy.

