##### **7.4.2.3 Time to First Negative Blood Culture**

Time to first negative blood culture is defined as the number of days from first dose date of study drug to the date of first negative blood culture plus 1.

Time to first negative blood culture will be summarized in total using descriptive statistics for the MITT and PP Population.

In addition, the Kaplan-Meier estimate of the median time to first negative blood culture and the associated 95% confidence interval will be presented. Patients without a negative blood culture at post-baseline visits will be censored at the last assessment date.

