#### **7.4.2.5 DRC Assessments**

Reasons for EOST failure according to DRC classifications (i.e. because (i) Blood cultures and/or cultures from other sites did not become negative at EOST, (ii) *Candida* infection spread to other sites, (iii) Additional antifungals given, (iv) Patient died, (v) Patient withdrew from study but did not die, or (vi) Other), will be summarized descriptively at the EOST visit for the MITT and PP populations. Once a patient has failed treatment, they are subsequently evaluated only for survival and for relevant safety parameters.

Reasons for relapse, or other reasons for not having an outcome of sustained success at follow-up according to DRC classifications, will be summarized descriptively at 2 and 4 weeks after EOST for the MITT and PP populations. Once a patient has relapsed, or has been assessed as a non-sustained success for any reason, they are subsequently evaluated only for survival and for relevant safety parameters.

Reasons for death according to DRC classifications (i.e. Candidemia/invasive candidiasis probably contributory, candidemia/invasive candidiasis probably not contributory, or not known) will be tabulated for the MITT and PP populations.

Factors that can affect outcome, such as intravascular catheter management (timely removal of lines), will be also be summarized descriptively.

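### Time to first negative blood culture censors patients who die uncleared and sets no rule for cultures taken after another antifungal, so the Kaplan-Meier median can be too short

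*SAP*

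**What the plan says.** SAP 6.2 lists time to first negative blood culture first among the secondary endpoints. SAP 7.4.2.3 defines it as "the number of days from first dose date of study drug to the date of first negative blood culture plus 1". Two summaries are planned. The endpoint "will be summarized in total using descriptive statistics for the MITT and PP Population", and in addition "the Kaplan-Meier estimate of the median time to first negative blood culture and the associated 95% confidence interval will be presented". The only rule for patients without the event is: "Patients without a negative blood culture at post-baseline visits will be censored at the last assessment date". The section mentions neither death nor another antifungal.

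Other parts of the documents bear on both:

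- Protocol 3.1 foresees rescue: "In the event of an inadequate response/failure on APX001 study treatment, the study drug may be discontinued and alternative antifungal treatment instituted".
- Protocol 6.5.3 still takes a blood culture after some patients stop: "For patients who are withdrawn from the study prior to completion, all EOST procedures will be performed at an Early Termination visit".
- SAP 6.4.1 makes Treatment Success conditional on being alive at EOST and on "No concomitant use of any other systemic antifungal therapies through EOST". Eradication carries a similar condition on other antifungals.
- SAP 7.4.2.5, under DRC Assessments, states: "Once a patient has failed treatment, they are subsequently evaluated only for survival and for relevant safety parameters". It lists additional antifungals among the reasons for failure.
- Protocol 4.4 says that patients who fail and start an alternative are assessed for safety 4 weeks after stopping study drug.
- SAP 7.1.2 keeps dropouts and patients with missing outcomes in the efficacy denominator and carries an earlier failure forward, but it does not say how this applies to a time-to-event endpoint.

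**The concern.** Kaplan-Meier is valid when a censored patient could still have the event and has the same prospects as those who remain under observation. A patient who dies uncleared meets neither condition. Removing that patient from the risk set raises the estimated clearance curve and can shorten the median read from it. Deaths are foreseeable here: the protocol describes high mortality and makes Day-30 mortality a secondary endpoint.

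The same question arises for a patient who stays positive on APX001 and starts another antifungal. If a later negative counts, the time includes the effect of the other drug. If the patient is censored at rescue, the analysis assumes that clearance on APX001 would have followed at the rate seen in patients who were responding.

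This is the only measure of speed of clearance in an uncontrolled study of about 15 patients, so each patient moves the estimate visibly. A short median could stand beside a primary analysis that counts many of the same patients as failures.

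**Working it through.** **Inputs.** The event, censoring rule and estimator come from SAP 7.4.2.3, and the sample size of about 15 from SAP 5. The documents give no clearance, death or rescue rate and no planned median, so there is no figure to reproduce. All patient data below are assumed.

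**Example A, deliberately adverse.** Of 15 patients with candidemia, 7 clear on APX001 on Days 2, 2, 3, 3, 4, 5 and 6. Four die uncleared, with last cultures on Days 1, 2, 3 and 3. Four start another antifungal and have a first negative on Days 7, 8, 8 and 9. The estimator is S(t) = product of (1 − events / at risk). Reading SAP 7.4.2.3 literally:

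| Day | At risk | Negatives | Censored after | S |
|---|---|---|---|---|
| 1 | 15 | 0 | 1 | 1.000 |
| 2 | 14 | 2 | 1 | 0.857 |
| 3 | 11 | 2 | 2 | 0.701 |
| 4 | 7 | 1 | 0 | 0.601 |
| 5 | 6 | 1 | 0 | 0.501 |
| 6 | 5 | 1 | 0 | 0.401 |
| 7 | 4 | 1 | 0 | 0.301 |
| 8 | 3 | 2 | 0 | 0.100 |
| 9 | 1 | 1 | 0 | 0.000 |

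The median is Day 6 and the curve reaches 100% cleared. Changing the rules one at a time gives:

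- Deaths held as not cleared, negatives after rescue still counted: 7/15 = 46.7% by Day 6 and 8/15 = 53.3% by Day 7, so the median is Day 7. The final figure is 11/15 = 73.3%.
- Rescued patients held as not cleared, deaths still censored: S stays at 0.401 from Day 6, so the median remains Day 6.
- Both held as not cleared: 7/15 = 46.7%, and the median is not reached.
- Rescued patients censored on Day 5, deaths censored: at risk on Day 6 is 6 − 1 − 4 = 1, so S(6) = 0. The curve reaches 100% and the median is Day 6.
- Rescued patients censored on Day 4, deaths censored: at risk on Day 5 is 7 − 1 − 4 = 2, so S(5) = 0.601 × 1/2 = 0.301 and the median falls to Day 5.

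The last two lines show that censoring at rescue does not cure the problem.

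**Example B, milder.** Clearance days are 2, 2, 3, 3, 3, 4, 4, 5, 6, 7, 8 and 10, with three deaths uncleared on Day 3. Kaplan-Meier gives S(3) = 10/15 = 0.667 and S(4) = 0.667 × 5/7 = 0.476, so the median is Day 4 and the curve reaches 100%. With death as a competing event, 7/15 = 46.7% are cleared by Day 4 and 8/15 = 53.3% by Day 5. The median is Day 5 and the final figure is 12/15 = 80.0%. If two of the twelve cleared only after rescue, clearance on APX001 is 10/15 = 66.7%, with median Day 5. The literal result is unchanged. Over 1 to 5 deaths and 0 to 3 rescues built the same way, the literal curve always ends at 100%, against 93.3% down to 46.7%. The medians differ by at most 1 day, except that with 5 deaths and 3 rescues the corrected median is not reached.

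**Simulation.** Settings: n = 15 and 3,000 runs each; underlying median clearance 3, 5 or 7 days; 10% to 30% die uncleared on Days 2 to 10; 0% to 20% clear only after rescue on Days 8 to 14.

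| Underlying median (days) | Deaths | Rescue | Day-14 cleared, Kaplan-Meier | Day-14 cleared, competing events | Typical medians (days) |
|---|---|---|---|---|---|
| 3 | 10% | 0% | 0.937 | 0.863 | 4 v 4 |
| 5 | 20% | 0% | 0.808 | 0.688 | 7 v 8 |
| 7 | 30% | 0% | 0.671 | 0.524 | 10 v 13 |
| 5 | 20% | 20% | 0.871 | 0.516 | 9 v 13 |
| 7 | 30% | 20% | 0.782 | 0.374 | 11 v not reached |

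Across all settings without rescue, the Day-14 gap runs from 0.727 − 0.675 = 5.2 points to 0.865 − 0.672 = 19.3 points. If negatives after rescue are counted, it runs from about 16 to 47 points. The typical median moves by 0 to 3 days when deaths and rescues together make up 30% or less, and by 1 to 8 days at 40%. At 50% the pairs are 8 v 27, 10 v 42, and 11 v not reached.

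**The case against.** A reader might infer that the SAP counts a negative obtained on another drug as an APX001 clearance. The documents do not support this as a stated rule. SAP 7.4.2.3 is silent on rescue, while SAP 7.4.2.5 and Protocol 4.4 point towards survival and safety follow-up only. The Early Termination visit is for patients withdrawn from the study, and the EOST culture may precede rescue. What stands is that 7.4.2.3 sets no cut-off and does not refer to 7.4.2.5, whereas Treatment Success and Eradication state their antifungal condition outright. A programmer following 7.4.2.3 has no instruction to exclude such a culture.

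A reader might also infer that patients who die are credited with clearance. They are not: a censored death is not an event. The estimated curve is inflated, which is a weaker statement. Nor does every planned summary favour the drug. In Example A, adding the four negatives after rescue to the observed times lengthens the mean from 25/7 = 3.6 to 57/11 = 5.2 days.

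Example A also sits on a threshold. Had one of the four rescued patients cleared on APX001 on Day 6 instead, 8/15 = 53.3% would have cleared and the fully corrected median would again be Day 6. The SAP plans a median and its interval, not a percentage cleared, so the 100% figures describe the underlying curve and not a planned output. Failure reasons, Day-30 survival and concomitant systemic antifungals are reported elsewhere, so a careful reader could see the deaths and rescues. These points limit the size of the concern. They do not make censoring at death uninformative.

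**Conclusion.** The concern holds as a modest flaw in a descriptive secondary endpoint. Censoring uncleared deaths follows from the rule as written, inflates the estimated clearance curve and can shorten the median. The handling of cultures after rescue is unspecified and not reconciled with SAP 7.4.2.5 or with the conditions in SAP 6.4.1. Censoring at rescue would not remove the bias.

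The size rests wholly on assumed clearance, death and rescue patterns. The median will often change little, and it becomes unreached only if about half or more of the patients die or are rescued uncleared. The proportion cleared is more sensitive than the median, even with deaths alone. The primary analysis is untouched, and no test, error rate or sample size depends on this endpoint.

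**What to change.** Amend SAP 7.4.2.3 as follows:

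1. Count a negative blood culture as an event only if it was collected after the first APX001 dose and before the first dose of any other systemic antifungal.
2. Treat death without clearance, and start of another systemic antifungal before clearance, as competing events. Report the cumulative incidence of clearance and take the median from it. Keeping these patients as not cleared to the end of the 42-day treatment period is equivalent when nobody is censored for another reason.
3. Report the numbers who died and who were rescued before clearance beside the median.
4. Refer to SAP 7.4.2.5 so that the two sections agree.

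The cost is SAP wording and minor programming before database lock. Culture, death and medication dates are already collected. The price in the results is that the reported median may be longer or may not be reached.

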#### **7.4.2.4 Overall Survival at Study Day 30**

Overall survival at Study Day 30 is defined as patient alive through study Day 30.

The number of percentage of patients alive or dead through Study Day 30 will be summarized for the MITT and PP Population.

Time to death is defined as the number of days from first dose date of study drug to the date of death from any cause plus one.. Patients who were not known to die, or were lost to follow-up will be censored on the last date the patient is known to be alive. The Kaplan-Meier estimate of the median time to death and the associated 95% confidence interval will be presented.

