4.4 Withdrawal Criteria

Study drug dosing may be discontinued for any of the following reasons:

- The patient withdraws consent or requests discontinuation from the study for any reason
- Occurrence of any medical condition or circumstance that exposes the patient to substantial risk and/or does not allow the patient to adhere to the requirements of the protocol
- Occurrence of significant drug-induced liver injury (DILI) [\[Appendix D\]](#)
- Any SAE, clinically significant adverse event, severe laboratory abnormality, intercurrent illness, or other medical condition that indicates to the Investigator that continued participation is not in the best interest of the patient
- Pregnancy
- Requirement of prohibited concomitant medication
- Patient failure to comply with protocol requirements or study-related procedures
- Termination of the study by the Sponsor or the regulatory authority
- Patients who discontinue study drug due to withdrawal of consent, death, or loss to follow-up will discontinue study participation. Patients who fail on study treatment and start alternative antifungals will be assessed for safety 4 weeks after stopping study medication. Patients who discontinue study drug for other reasons will enter the follow-up phase of the study.

If a patient withdraws prematurely from the study due to any of the above criteria or for any other reason, study staff should make every effort to contact the Sponsor prior to discontinuation, if possible, and to complete the full panel of assessments scheduled for the Early Termination Visit. The reason for patient withdrawal must be documented in the eCRF.

In the case of patients lost to follow-up, attempts to contact the patient must be made and documented in the patient's medical records.

Withdrawn patients will not be replaced.

The study may be discontinued for any of the following reasons: five or more subjects in study (cumulative) experience a same Grade 2 (or higher) related AE (laboratory or systemic) which is coded in the same high-level group term per MedDRA coding, throughout the duration of study; a recommendation from the DSMB based on other safety signals; lack of Investigational Product availability; inability to enroll the study; or decision by a regulatory authority or the sponsor.

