#### **6.2 Secondary Efficacy Endpoints**

The secondary efficacy parameters include the following:

- Time to first negative blood culture;
- Percentage of patients with successful Mycological Outcomes at EOST, and at 2 and 4 weeks after EOST;
- Percentage of patients with Treatment Success at EOST as determined by the investigator;
- Percentage of patients with Treatment Success 2 and 4 weeks after EOST, as determined by the investigator and the DRC;

- All-cause mortality at Study Day 30; and
- Number of patients with TEAEs.

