### **7.1.2 Handling of Dropouts and Missing Data**

Subjects who dropped out or had missing outcome data will be included in the denominator for efficacy analyses. A clinical failure occurring at an earlier time point will be carried forward to the subsequent visits.

In cases of missing or incomplete dates (e.g. Adverse event [AE] and concomitant medications), the missing component(s) will be assumed as the most conservative value possible. For example, AEs with missing start dates, but with stop dates either overlapping into the treatment period or missing, will be counted as treatment-emergent, taking the worst-case approach. When partial dates are present in the data, both a partial start date and/or a partial stop date will be evaluated to determine whether it can be conclusively established that the AE started prior to the start of study drug or ended prior to the start of study drug. If the above cannot be conclusively established based on the partial and/or present dates, then the AE will be considered as treatment-emergent. Actual data values as they appear in the original eCRF will be presented in the data listings.

Missing values for other variables will not be imputed and only observed values will be used in data analyses and summaries.

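### Day-30 all-cause mortality has no confidence interval and no stated category for unknown vital status, and the planned Kaplan-Meier curve is read only at its median

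*SAP*

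**What the plan says.** Protocol 7.2 and SAP 6.2 list all-cause mortality at Study Day 30 as a secondary efficacy endpoint. SAP 7.4.2.4 turns it into a survival endpoint: "Overall survival at Study Day 30 is defined as patient alive through study Day 30". The planned table is: "The number of percentage of patients alive or dead through Study Day 30 will be summarized for the MITT and PP Population". No interval is mentioned.

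The same section defines time to death from the first dose. Patients not known to have died, or who "were lost to follow-up will be censored on the last date the patient is known to be alive". One quantity is requested from that analysis: "The Kaplan-Meier estimate of the median time to death and the associated 95% confidence interval will be presented".

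The general missing-data rules are in SAP 7.1.2. For efficacy: "Subjects who dropped out or had missing outcome data will be included in the denominator for efficacy analyses". An earlier clinical failure is carried forward. The section ends: "Missing values for other variables will not be imputed and only observed values will be used in data analyses and summaries".

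By contrast, a two-sided 95% exact binomial interval is specified for:
- Treatment Success at EOST as judged by the Data Review Committee (SAP 7.4.1);
- investigator-judged success at EOST, and sustained success at 2 and 4 weeks (SAP 7.4.2.1);
- eradication and presumed eradication at EOST (SAP 7.4.2.2).

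**The concern.** In an open-label, single-arm study of about 15 patients, death is the efficacy outcome least open to judgement. Three features of its planned analysis fall short.

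1. **No interval.** A mortality percentage from 15 patients is very imprecise, and the table will not show it, although neighbouring tables show it for softer outcomes.
2. **No category for unknown status.** The table has two rows. A patient lost before Day 30 stays in the denominator but belongs in neither row. The percentage dead then treats that patient as not dead. The closing sentence of SAP 7.1.2, on using observed values only, could also be read as permitting exclusion. Nothing prespecified decides between these readings.
3. **The curve is read at the wrong place.** Kaplan-Meier with censoring handles patients whose status becomes unknown, and it is already planned. Its only named output is the median time to death, not the probability of death by Day 30.

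At stake is whether the reported Day-30 mortality is understated, and whether its uncertainty is visible.

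**Working it through.** The plan states no mortality rate, precision target or formal sample-size calculation, so there is no figure of its own to reproduce.

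**Inputs.** N is about 15 (SAP 5). The interval type is two-sided 95% exact binomial (SAP 7.4.1). Treatment lasts up to 42 days and follow-up a further 4 weeks (+4 days) (SAP 2.2), so the survival curve can run to 42 + 28 = Day 70, or Day 74 with the window. The numbers of deaths and unknowns below are assumptions for illustration.

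**Step 1: the missing interval.** Clopper-Pearson 95% limits for deaths out of 15:

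| Deaths | Mortality | 95% exact CI |
|---|---|---|
| 0 | 0% | 0 to 21.8% |
| 3 | 20.0% | 4.3 to 48.1% |
| 4 | 26.7% | 7.8 to 55.1% |
| 5 | 33.3% | 11.8 to 61.6% |
| 7 | 46.7% | 21.3 to 73.4% |

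**Step 2: unknown status.** Assume 4 known deaths and 2 unknowns among 15, leaving 9 known alive.

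| Handling of the 2 unknowns | Mortality | 95% exact CI |
|---|---|---|
| In denominator, not counted dead | 4/15 = 26.7% | 7.8 to 55.1% |
| Excluded | 4/13 = 30.8% | 9.1 to 61.4% |
| Counted dead | 6/15 = 40.0% | 16.3 to 67.7% |

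In the first case the table shows 26.7% dead and 9/15 = 60.0% alive; the other 2/15 = 13.3% are in neither row. Each unknown patient is worth 1/15 = 6.7 points.

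**Step 3: what the planned curve would give at Day 30.** Assume deaths on Days 3, 8, 14 and 22 and losses on Days 5 and 10. The numbers at risk at the four deaths are 15, 13, 11 and 10.

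S(30) = 14/15 × 12/13 × 10/11 × 9/10 = 0.705, so Day-30 mortality is 29.5%.

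Greenwood sum = 1/(15×14) + 1/(13×12) + 1/(11×10) + 1/(10×9) = 0.0314. The log-log standard error is √0.0314 / |ln 0.705| = 0.507. The 95% interval for mortality is 1 − 0.705^exp(∓1.96×0.507), which is 12.2 to 61.1%.

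**Step 4: can the median be estimated?** With 15 patients and no early censoring, the curve reaches 0.5 only after 8 deaths. P(X ≥ 8) for X ~ Binomial(15, p), with p the cumulative mortality over follow-up:

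| p | 20% | 30% | 40% | 50% | 60% |
|---|---|---|---|---|---|
| P(median reached) | 0.004 | 0.050 | 0.213 | 0.500 | 0.787 |

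The curve is not cut at Day 30, so later deaths count too. A simulation of 15 patients used 4,000 runs per case, follow-up of 44 to 70 days and no losses. The hazard after Day 30 was either 0.3 times the earlier one or unchanged (lower and upper figures):

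| Assumed Day-30 mortality | Median reached | Upper 95% limit estimable |
|---|---|---|
| 20% | 4 to 22% | 0.3 to 2% |
| 30% | 20 to 59% | 1 to 8% |
| 40% | 49 to 87% | 5 to 30% |
| 50% | 77 to 98% | 19 to 63% |
| 60% | 94 to over 99% | 50 to 89% |

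Whether the median appears therefore depends on a rate the documents do not give. In none of these cases does it estimate Day-30 mortality.

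**The case against.** The best defence is that this is a small descriptive study. Protocol 9.2.1.2 asks only for a descriptive summary of Day-30 survival, and the SAP supplies one. There is no hypothesis or precision target. Not every secondary rate has an interval: recurrence at 2 and 4 weeks has none. A reader can compute an exact interval from n/N. That much stands, and it keeps the point modest. It does not settle how unknowns are counted, which a reader cannot recover without knowing how many there were.

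Three stronger readings are tempting and are not supported.

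- *The median will usually not be reached.* The protocol's introduction says only that mortality is high, and the curve runs well past Day 30. At 40% Day-30 mortality the median is reached in 49 to 87% of simulated trials. Its upper limit is often missing, but that is a smaller complaint.
- *Unknown status is ignored.* SAP 7.1.2 keeps these patients in the denominator and SAP 7.4.2.4 censors them. The gap is the undefined category in the Day-30 table.
- *Follow-up stops short of Day 30.* Patients who fail and start another antifungal "will be assessed for safety 4 weeks after stopping study medication" (Protocol 4.4), so one might infer that a patient stopping on Day 1 is last seen on Day 29. The 4-week visit has a +4-day window (Protocol Appendix A). Serious adverse events, including death, are reported until 30 days after the last dose (Protocol 8.3). SAP 7.4.2.5 continues survival evaluation after failure. Protocol 4.4 requires documented attempts to contact patients lost to follow-up.

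Unknowns should therefore be few, mainly consent withdrawals and true losses, for whom Protocol 4.4 ends participation.

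**Conclusion.** The point holds in a limited form. The named Day-30 endpoint lacks an interval that comparable rates receive, and the classification of unknown vital status is left open. Under the denominator rule, the percentage dead leans towards understating mortality. In the illustration, the choice of rule moves the result from 26.7% to 40.0%, and the Kaplan-Meier estimate is 29.5%. The spread is within the sampling uncertainty (7.8 to 55.1% for 4/15), but it is a systematic lean in one direction and avoidable. If every patient's Day-30 status is known, only the missing interval remains.

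The illustration rests on assumed counts and dates. The Kaplan-Meier estimate also assumes that losses are unrelated to the risk of death, which is why a worst-case analysis belongs beside it. A SAP correction is worth making; nothing here suggests a flaw in the conduct of the study.

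**What to change.** In SAP 7.4.2.4:

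1. Report the Kaplan-Meier estimate of all-cause mortality at Study Day 30 with a 95% confidence interval, from the curve and censoring rule already defined there.
2. Give the crude Day-30 mortality with a two-sided 95% exact binomial interval, as for the success rates.
3. Add an unknown-vital-status row, so that the categories sum to N.
4. Add a sensitivity analysis counting unknown status as dead.
5. Keep the median time to death if wanted, shown as not reached where that applies.

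The cost is a few lines of SAP text and a little more output. SAP 1 has the plan finalised before database lock, so the change belongs before then. Stated mortality may come out slightly higher. No added Day-30 contact is proposed: it would be a protocol procedure needing an amendment under Protocol 12.1, and the existing follow-up leaves few patients for whom it would matter.
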